6.2.2.2. Caregiver Global Impression of Improvement Scale

CaGI-I is single item questionnaire to assess the caregiver's impression of improvement in dyskinesia symptoms after initiating therapy. It is to be completed before all other investigator-rated scales during visits where CaGI-I is collected. The caregiver has to select the 1 response from the response options that gives the most accurate description of change in dyskinesia symptoms of the patient they care for from the beginning of the study:

- 1=very much improved (since the initiation of treatment in this study);
- 2=much improved;
- 3=minimally improved;
- 4=no change from day 1 (symptoms remain essentially unchanged);
- 5=minimally worse;
- 6=much worse;
- 7=very much worse (since the initiation of treatment).

The CaGI-I is a single item questionnaire, no impute is used.

The actual value in CaGI-I to each post-baseline visit will be summarized.

6.2.2.3. Clinical Global Impression of Improvement Scale

The Clinical Global Impression of Improvement (CGI-I) is a clinician-reported outcome that uses a 7-point Likert scale that allows the clinician to compare the patient's condition at the visit to the day 1 condition as follows (with anchor points for choosing the most appropriate improvement level):

- 1=very much improved since the initiation of treatment in this study (nearly all better; good level of functioning; minimal symptoms; represents a very substantial change);
- 2=much improved (notably better with significant reduction of symptoms; increase in the level of functioning but some symptoms remain);

3=minimally improved (slightly better with little or no clinically meaningful reduction of symptoms; represents very little change in basic clinical status, level of care, or functional capacity);

4=no change from day 1 (symptoms remain essentially unchanged);

5=minimally worse (slightly worse but may not be clinically meaningful; may represent very little change in basic clinical status or functional capacity);

6=much worse (clinically significant increase in symptoms and diminished functioning);

7=very much worse since the initiation of treatment in this study (severe exacerbation of symptoms and loss of functioning).

The CGI-I is a single item questionnaire, no imputation is used.

The actual value in CGI-I to each post-baseline visits will be summarized.

6.2.2.4. Clinical Global Impression of Severity

The Clinical Global Impression of Severity (CGI-S) uses a 7-point Likert scale to assess dyskinesia severity as follows (with anchor points for choosing the most appropriate severity level caused by DCP):

1=normal (not at all ill, symptoms of disorder not present past 7 days);

2=borderline (subtle or suspected pathology);

3=mild (clearly established symptoms with minimal, if any, distress or difficulty in social and/or occupational function);

4=moderate (overt symptoms causing noticeable, but modest, functional impairment or distress; symptom level may warrant medication);

5=marked (intrusive symptoms that distinctly impair social/occupational function or cause intrusive levels of distress);

6=severe (disruptive symptoms, behavior and function are frequently influenced by symptoms, may require assistance from others);

7=extreme (symptoms drastically interferes in many life functions; may be hospitalized).

The CGI-S is a single item questionnaire, no imputation is used.

6.2.2.5. Pediatric Evaluation Disability Inventory-Computer Adapted Test (Activities of Daily Living, Caregiver Completed, Content-Balanced Version)

The PEDI-CAT (activities of daily living [ADL], parent/caregiver completed, content balanced version) is a clinical assessment for children and youth. It measures function in 4 domains: (1) Daily Activities; (2) Mobility; (3) Social/Cognitive, and (4) Responsibility. Each domain is self-contained and can be used separately or with other domains. The content balanced version presents a balance of items from each of the Daily Activities domain's content areas (Getting Dressed, Keeping Clean, Home Tasks, and Eating & Mealtime). A total of approximately 30 items are administered (total number of items administered is dependent upon the responses and decision tree path). The PEDI-CAT software utilizes Item Response Theory statistical models to

estimate a child's abilities from a minimal number of the most relevant items or from a set number of items within each domain. All respondents begin with the same item in each domain in the middle of the range of difficulty or responsibility and the response to that item then dictates which item will appear next (a harder or easier item), thus tailoring the items to the child and avoiding irrelevant items. The CAT program then displays the results: normative standard scores, scaled scores and the SE. The scales are available for 21 age groups as intervals of 1 year.

Normative (fit) scores are based on a child's chronological age and intended for use by clinicians so that they may interpret a particular child's functioning relative to others of the same age. This metric is of less relevance for the studied population and therefore will not be assessed.

Scaled scores provide a way to look at a child's current functional skills and progress in these skills over time. Scaled scores are especially helpful in documenting improvements in functional skills for children not expected to exhibit or regain normative levels of functioning. The scaled scores are based on an estimate of the placement of an individual child along the hierarchical scale within each domain. The PEDI-CAT scaled scores are currently on a 20 to 80 scale metric. See PEDI-CAT (Version 1.3.6) Development, Standardization and Administration Manual.

The SE scores indicate the level of the test precision, and are expected to be up to 0.5.

A descriptive summary of the PEDI-CAT scaled score will be provided for all measurements and change from baseline.

6.2.2.6. Unified Huntington's Disease Rating Scale-Total Motor Score

UHDRS-TMS comprises a broad assessment of features associated with Huntington's Disease. The TMS component of UHDRS comprises 31 assessments from the 15 items of the UHDRS. The TMS is calculated as the sum of the 31 motor assessments, each of which range between 0 to 4. The minimum score is 0 (absent) and the maximum score is 124 (worst).

UHDRS-TMC is part of the UHDRS-TMS assessment and assesses the severity of chorea in the face, mouth, trunk, and the 4 extremities. The minimum score is 0 (absent), and the maximum score is 28 (marked/prolonged).

UHDRS-TMD is part of the UHDRS-TMS assessment and assesses the severity of dystonia in the trunk and the 4 extremities. The minimum score is 0 (absent), and the maximum score is 20 (marked/prolonged).

If responses of up to 25% of items are missing in UHDRS-TMS, UHDRS-TMC, or UHDRS-TMD ("scale"), the missing responses will be replaced by the average of the remaining responses within each of the scales. If 8 or more of the items are missing, the missing items will not be replaced and the scale will be set to missing.

The actual values and change from baseline for the UHDRS-TMS, TMC and TMD will be summarized.

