## **Section 6 Assessments of Efficacy**

In the event of an emergency situation (eg, the COVID-19 pandemic), in case a patient cannot return to the clinic for the scheduled visits (eg, due to quarantine, isolation, patient's concern, or closure of the site clinic), remote assessment may be allowed for the following:

- via nonrecording live video for the Clinical Global Impression of Improvement [CGI-I] mandatory at week 3 and week 7, Clinical Global Impression of Severity [CGI-S], Movement Disorder-Childhood Rating Scale [MD-CRS] parts I and II, Unified Huntington's Disease Rating Scale-Total Motor Score [UHDRS-TMS], and the Canadian Occupational Performance Measure [COPM], as applicable. The results of the questionnaires will be entered to the case report form (CRF) per the usual process indicating that the rating has been performed remotely.
- via iPhone® (Apple, Inc) or via paper back-up copy instead of iPad® (Apple Inc) for the Caregiver Global Impression of Improvement [CaGI-I] and the Pediatric Evaluation Disability Inventory-Computer Adapted Test [PEDI-CAT], as applicable. The results of the questionnaires will be transferred to the CRF per the usual process (either from iPhone or from paper back-up copy).

The MD-CRS Part I & II are optional at the investigator's discretion and may be incomplete considering patient's imbalance when standing and walking and prioritizing patient safety. UHDRS-TMS should be completed as much as possible; some fields (ie, rigidity, stability) may be left blank as they cannot be assessed remotely. The pull test should not be done due to safety considerations.

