4.3. Handling Withdrawals and Missing Data

For most variables, only observed data from the patients will be used in the statistical analyses, ie, there is no plan to impute missing data for these variables, unless otherwise specified.

Rules for handling missing items in efficacy and safety rating scales/questionnaire are presented in Section 6.2.2 and Section 8.

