	VII.4. School problems	'Yes'=0, 'No'=1.

Values of 'Do not know', 'Not applicable', or 'Has no brothers or sisters' will be ignored for mean calculations and logically skipped items will be imputed as 0 or none.

A subscale score is calculated as the sum of the item scores and the total score is calculated as the sum of the subscale scores. If one or more subscale scores are missing, the total score will not be calculated.

If 1 item from activities and social subscales has a missing value, the mean of the other items of that subscale is substituted for that item. If more than 1 item is missing from either of these scales or any item is missing from the school scale, the respective scale is not to be scored.

Results will be listed.

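### The 8-item set-to-missing cut-off for the UHDRS scores cannot be reached on the 7-item chorea or 5-item dystonia score, so 2–6 or 2–4 missing items have no stated outcome

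*SAP*

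**What the plan says.** SAP 6.2.2.6 gives one missing-item rule for three UHDRS scores. It opens with "If responses of up to 25% of items are missing in UHDRS-TMS, UHDRS-TMC, or UHDRS-TMD" and, in that case, fills the gaps with the mean of the items observed on the same scale. It then sets the limit beyond which no score is given: "If 8 or more of the items are missing, the missing items will not be replaced and the scale will be set to missing".

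The same section defines the scales. TMS is the sum of 31 assessments, each scored 0 to 4, with a maximum of 124. TMC "assesses the severity of chorea in the face, mouth, trunk, and the 4 extremities" and has a maximum of 28. TMD "assesses the severity of dystonia in the trunk and the 4 extremities" and has a maximum of 20.

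The general rule in SAP 4.3 uses observed data: "there is no plan to impute missing data for these variables, unless otherwise specified". It refers item-level rules to Sections 6.2.2 and 8. Protocol 9.3 likewise limits the analyses to observed data. Neither says whether a total with some items missing counts as a score.

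**The concern.** A percentage limit and an absolute count are used side by side for scales of very different length. If the count matches the percentage on only one of them, the other two are left with a range in which items may not be replaced but nothing makes the score missing.

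What would be at stake is the value entered for a patient with a partly completed chorea or dystonia rating. One programmer would set it to missing and another might add up what is there. A partial sum reads as milder disease. In a change from baseline it would look like improvement if the items were missing after baseline, and like worsening if they were missing at baseline. TMC and TMD, each physician-rated and centrally read, make up four of the fifteen efficacy endpoints in SAP 6.2.1, and the protocol (3.3) describes a population in which chorea predominates.

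**Working it through.** **Inputs (all SAP 6.2.2.6).** Item range 0–4; maxima 124 (TMS), 28 (TMC) and 20 (TMD); replacement up to 25% of a scale's items; set to missing at 8 or more items.

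**Item counts.** n = maximum / 4. This gives TMS 31, as the SAP states. TMC has 7 (face, mouth, trunk and four extremities: 1 + 1 + 1 + 4). TMD has 5 (trunk and four extremities: 1 + 4).

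**Rule by scale.** The largest replaceable count is 0.25 × n rounded down. Counts above that and below 8, with at least one item observed, are covered by neither sentence.

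| Scale | n | 25% of n | Replaced | Covered by neither | Set to missing by the count of 8 |
|---|---|---|---|---|---|
| TMS | 31 | 7.75 | 1–7 (7/31 = 22.6%) | none | 8 or more (8/31 = 25.8%) |
| TMC | 7 | 1.75 | 1 (1/7 = 14.3%) | 2–6 (28.6% to 85.7%) | never, since 8 > 7 |
| TMD | 5 | 1.25 | 1 (1/5 = 20.0%) | 2–4 (40.0% to 80.0%) | never, since 8 > 5 |

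The plan's figure of 8 is therefore reproduced exactly for TMS: it is the first count above 25% of 31. On TMC, 5 of the 7 possible non-zero missing counts have no rule, and on TMD 3 of 5. With all items missing there is nothing to score in any case.

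**Another reading.** Suppose the 8 is counted across all 31 TMS assessments. A patient with 2–6 chorea items or 2–4 dystonia items missing, and fewer than 8 missing overall, still has no rule. Nor can this reading apply to the centrally read TMC and TMD, because TMS is not centrally read.

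**Illustration of a partial sum.** Assume every item scores 2 and two items are missing.
- TMC: 5 × 2 = 10 instead of 7 × 2 = 14, short by 4/14 = 28.6%.
- TMD: 3 × 2 = 6 instead of 5 × 2 = 10, short by 4/10 = 40%.

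In general the shortfall with two items missing is 2 × the item score: 2, 4 or 6 points for item scores of 1, 2 or 3.

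**Do other SAP rules settle the intent?** They differ from scale to scale:
- MD-CRS totals are rescaled for any number of missing items (6.2.2.1).
- ESRS items are replaced with no stated limit (8.14).
- ESS is void with one item missing (8.13), and so is a CBCL Syndrome subscale (8.12.2).
- CBCL Activities and Social, six items each, are the nearest in form (8.12.1): "If 1 item from activities and social subscales has a missing value, the mean of the other items of that subscale is substituted" (1/6 = 16.7%). The next step follows without a gap: "If more than 1 item is missing from either of these scales or any item is missing from the school scale", the scale is not scored (2/6 = 33.3%).

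The CBCL Competence rule shows the structure that the UHDRS rule lacks, but with this much variety no single rule can be carried over by analogy.

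**The case against.** Nothing in the SAP tells anyone to report a partial sum. The section defines TMC over seven regions and TMD over five, so a sum over fewer is arguably not that score. The 25% limit already separates replaced from not replaced on every scale, and setting the score to missing is the natural reading of what follows. This stands as to probable intent. It does not supply the rule: the only sentence that sets a score to missing uses a count that two of the three scales cannot reach, so read literally a TMC with six of seven items absent is not set to missing.

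Nor do the documents show a route to the gap. It takes at least two blank chorea or dystonia items within a rating that was otherwise done. For remote UHDRS ratings, protocol Appendix M says "some fields (ie, rigidity, stability) may be left blank as they cannot be assessed remotely", and those are not TMC or TMD items. Remote ratings use live video that is not recorded, so a remote visit points to an absent central reading rather than a partial one. Remote week 53/ET and week 54 assessments are to be repeated in clinic when conditions allow. All of this stands and limits how often the gap could matter.

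Finally, the study is single-arm and safety-oriented, with no hypothesis tests, and these are secondary measures. That also stands, and keeps the consequence low.

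**Conclusion.** The point holds. The cut-off of 8 is right for TMS and wrong for the other two scales it governs. It leaves 2–6 missing items on TMC and 2–4 on TMD without an outcome, and no other section of the SAP or protocol closes the gap.

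The item counts rest on the SAP's own maxima and region lists. The point shortfalls rest on assumed item scores and on someone summing observed items, which is a possible misreading rather than an instruction. No effect on group means is claimed, because the documents do not say how often chorea or dystonia items are missing. The primary safety objective is untouched. This should be corrected because the stated number is wrong for two scales and the correction is trivial, not because a large bias is expected.

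**What to change.** Replace the set-to-missing sentence in SAP 6.2.2.6 with one that applies the existing 25% limit to each scale:

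> If more than 25% of a scale's items are missing (TMS: 8 or more of 31; TMC: 2 or more of 7; TMD: 2 or more of 5), no item on that scale is imputed and the score for that scale is missing.

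This leaves TMS handling as it is, introduces no new threshold, and should apply to the physician-rated and centrally read TMC and TMD alike. It costs one sentence in a SAP amendment before database lock, with no new data and no effect on patients.

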6.2.2.7. Canadian Occupational Performance Measure

The COPM has been designed to assess patient outcomes in the areas of self-care, productivity and leisure. Using a semi-structured interview, each patient will identify 5 most important problem areas, and will evaluate performance and satisfaction related to those problem areas.

The COMP performance and satisfaction scale is range from 1 (poor performance or low satisfaction) to 10 (very god performance or high satisfaction).

Total scores are calculated by adding together the performance or satisfaction scores for all problems and dividing by the number of problems. Individual activity problems will be listed.

6.3. Subgroup Analyses

No efficacy subgroup analysis is planned.

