**Day 1: Between 2 and  $\leq$ 4 weeks after Study TV50717-CNS-30080 week 15 visit:**

If, in the judgment of the investigator, the patient has *not* had any clinically significant change since the week 15 visit of Study TV50717-CNS-30080 in health, concomitant medications, clinical assessments, laboratories, ECGs, or non-medical interventions, the patient will undergo all day 1 assessments outlined in [Table 4](#), except hematology, chemistry, and urinalysis laboratories and urine drug screen, which can be carried over from Study TV50717-CNS-30080 week 15 or week 16 visit, whichever is more current.

If, in the judgment of the investigator, the patient has had a clinically significant change since the week 15 visit of Study TV50717-CNS-30080 in health, concomitant medications, clinical assessments, laboratories, ECGs, or non-medical interventions, the patient will undergo all screening procedures outlined in [Table 4](#). Patients who remain eligible for participation in the study will be asked to return for day 1 assessments.

Study drug will be dispensed at day 1 once all procedures and investigator-related assessments are completed and patient eligibility is confirmed.

For patients who enroll in the study between 2 and  $\leq$ 4 weeks after the Study TV50717-CNS-30080 week 15 visit, the investigator is required to consult with the medical monitor regarding eligibility prior to baseline/day 1. The patient's file should include all related correspondence with the medical monitor.

**Titration period (7 weeks):** Because the patients from parent Study TV50717-CNS-30080 have discontinued TEV-50717 treatment for at least 1 week at completion of the parent study or received placebo in the parent study, all patients will undergo TEV-50717 dose titration in this study in order to maintain the blind of the parent Study TV50717-CNS-30080. Patients will receive 6 mg of TEV-50717 ([Table 2](#)). This dose will be administered in the morning on days 2 and 3, followed by evening administration starting on day 3 for the remainder of the week (if body weight is  $\geq$ 40 kg/88 lbs). TEV-50717 daily doses of 12 mg and higher will be administered

as 2 divided equal doses, approximately 8 to 10 hours apart during the day. A minimum of 6 hours should elapse between doses.

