**Day 1: Between 2 and  $\leq$ 4 weeks after Study TV50717-CNS-30080 week 15 visit:**

If, in the judgment of the investigator, the patient has *not* had any clinically significant change since the week 15 visit of Study TV50717-CNS-30080 in health, concomitant medications, clinical assessments, laboratories, ECGs, or non-medical interventions, the patient will undergo all day 1 assessments outlined in [Table 4](#), except hematology, chemistry, and urinalysis laboratories and urine drug screen, which can be carried over from Study TV50717-CNS-30080 week 15 or week 16 visit, whichever is more current.

If, in the judgment of the investigator, the patient has had a clinically significant change since the week 15 visit of Study TV50717-CNS-30080 in health, concomitant medications, clinical assessments, laboratories, ECGs, or non-medical interventions, the patient will undergo all screening procedures outlined in [Table 4](#). Patients who remain eligible for participation in the study will be asked to return for day 1 assessments.

Study drug will be dispensed at day 1 once all procedures and investigator-related assessments are completed and patient eligibility is confirmed.

For patients who enroll in the study between 2 and  $\leq$ 4 weeks after the Study TV50717-CNS-30080 week 15 visit, the investigator is required to consult with the medical monitor regarding eligibility prior to baseline/day 1. The patient's file should include all related correspondence with the medical monitor.

**Titration period (7 weeks):** Because the patients from parent Study TV50717-CNS-30080 have discontinued TEV-50717 treatment for at least 1 week at completion of the parent study or received placebo in the parent study, all patients will undergo TEV-50717 dose titration in this study in order to maintain the blind of the parent Study TV50717-CNS-30080. Patients will

receive 6 mg of TEV-50717 ([Table 6](#)). This dose will be administered in the morning on days 2 and 3, followed by evening administration starting on day 3 for the remainder of the week (if body weight is  $\geq 40$  kg/88 lbs). TEV-50717 daily doses of 12 mg and higher will be administered as 2 divided equal doses, approximately 8 to 10 hours apart during the day. A minimum of 6 hours should elapse between doses.

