2.5. Sample Size and Power Considerations

This study is open-label and safety oriented in nature; therefore, no formal hypothesis testing is planned. The sample size for this study is not based on statistical considerations; hence, only descriptive statistics will be presented.

Based on the number of patients in the parent study (Study TEV50717-CNS-30080) approximately 45 patients who completed the parent study may enroll in this study.

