8. SAFETY ANALYSIS

8.1. General

Safety analyses will be performed on the ITT analysis set, unless otherwise noted. Summaries will be presented by overall patients. Selected safety data might also be presented by age group, as applicable.

For continuous variables, descriptive statistics will be provided for actual values and changes from baseline to each time point. For categorical variables, patient counts and percentages will be provided.

Summaries of potentially clinically significant abnormal values will include all post-baseline values (including scheduled, unscheduled, and early termination visits).

Safety assessments and time points are provided in [Table 3](#).

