8.2. Duration of Exposure to Study Drug

Duration of exposure to study drug (days) for individual patients is the number of days patient received drug (last day of study drug – first day of study drug + 1). Duration of treatment (days) will be summarized using descriptive statistics. Weeks on treatment using the categories ≤ 4 weeks, >4 to ≤ 7 weeks, >7 to ≤ 21 weeks, >21 to ≤ 27 weeks, >27 to ≤ 33 , >33 to ≤ 40 , >40 to ≤ 46 , >46 to ≤ 53 , and >53 weeks will also be summarized using descriptive statistics.

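### Efficacy, adverse event, disposition and exposure summaries pool patients who took TEV-50717 in the parent study with patients who took placebo, so change from day 1 may mix two starting states and adverse event incidence mixes first exposure with re-exposure

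*SAP*

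**What the plan says.** Protocol section 3.1, under the titration period, gives the two origins of the patients. They have either "discontinued TEV-50717 treatment for at least 1 week at completion of the parent study or received placebo in the parent study". All are titrated again from the starting dose, and the stated reason is to protect the parent-study blind.

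The analysis plan does not use this distinction:

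- **Efficacy.** SAP 6.3: "No efficacy subgroup analysis is planned". SAP 6.1 uses the whole ITT set.
- **Safety.** SAP 8.1: "Summaries will be presented by overall patients". The only optional split is by age group. SAP 8.3 presents adverse events for all patients.
- **Population and disposition.** SAP 5.1 and 5.2 summarise all patients together. The baseline variables in SAP 5.3 include age group, weight group, region and CYP2D6 status, but not parent treatment.
- **Exposure.** SAP 8.2: "Duration of exposure to study drug (days) for individual patients is the number of days patient received drug", calculated from the first to the last day of study drug. Parent-study exposure is not added.
- **Baseline.** SAP 4.2 and 6.2 measure change from day 1 of this study or the parent week 16 visit, not from the parent pre-treatment baseline.

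SAP 8.11 does ask for C-SSRS frequencies by treatment, and protocol 7.2.1 by treatment group. Neither defines the term for a single-arm study, and protocol 9.6 asks for C-SSRS by visit only.

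**The concern.** The primary objective is long-term safety and tolerability, and entry requires completion of parent week 16. Prior-drug patients have therefore already been through a course of the drug and stayed to the end. Prior-placebo patients are taking it for the first time. An adverse event percentage over both groups describes neither, and washout does not remove this difference in history.

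For efficacy, a prior-drug patient may reach day 1 with some benefit left, with worsening after withdrawal, or with neither. Pooled change from day 1 is a change from an untreated state only in the last case.

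Two features of the plan show how this could enter the results. CGI-I, which guides titration, takes the week before day 1 as its reference (protocol 6.1.3); for a same-day rollover that is the washout week. For early rollovers, day 1 weight is carried over from parent week 16. Protocol 1.2.2.2 singles out weight gain as the exception to the known adult safety profile in long-term paediatric use, and any gain during the parent study would already be in that baseline.

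**Working it through.** **The plan's own figure.** SAP 2.5 says that "approximately 45 patients who completed the parent study may enroll in this study" and that "The sample size for this study is not based on statistical considerations; hence, only descriptive statistics will be presented". No effect size, SD, alpha or power is given, so there is no calculation to reproduce. I take N = 45.

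**Assumed inputs.** The parent allocation ratio is not in the documents. I assume 1:1 (22 prior drug, 23 prior placebo) and 2:1 (30 and 15). The fraction r of the drug effect still present at day 1 is not given either; I take 0, 0.25 and 0.5.

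**Change from day 1.** Let w be the prior-drug share and D the change from an untreated state, and suppose both groups reach the same on-treatment state. Prior-placebo patients change by D and prior-drug patients by (1 - r)D. Then

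pooled change / D = (1 - w) + w(1 - r) = 1 - wr.

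| r | w = 0.5 | w = 0.667 |
|---|---|---|
| 0 | 1.00 | 1.00 |
| 0.25 | 1 - 0.125 = 0.875 | 1 - 0.167 = 0.833 |
| 0.5 | 1 - 0.25 = 0.75 | 1 - 0.333 = 0.667 |

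The range is 67-100%. With no retained effect, pooling does no harm to the mean. A rebound makes r negative and the ratio exceeds 1: for example, r = -0.25 with w = 0.5 gives 1 + 0.125 = 1.125.

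**Adverse events.** The pooled incidence is the weighted mean of the two groups. If incidence were 40% in prior-placebo and 20% in prior-drug patients (assumed):

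- 1:1: (23 × 0.40 + 22 × 0.20)/45 = 13.6/45 = 30.2%
- 2:1: (15 × 0.40 + 30 × 0.20)/45 = 12/45 = 26.7%

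If the two incidences are equal, pooling changes nothing.

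**Precision after a split.** The one-sided 95% upper bound for an event not seen in n patients is 1 - 0.05^(1/n). The 95% half-width of a mean, in SD units, is t(0.975, n - 1)/√n.

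| n | upper bound, 0 events | half-width (SD) |
|---|---|---|
| 45 | 6.4% | 0.30 |
| 30 | 9.5% | 0.37 |
| 23 | 12.2% | 0.43 |
| 22 | 12.7% | 0.44 |
| 15 | 18.1% | 0.55 |

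The columns can describe but not test. That fits a study in which everything is descriptive.

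**The case against.** **Not everything is pooled or depends on day 1.** A reader might infer that every result is affected. The documents do not support that. C-SSRS has the undefined breakdown by treatment. Actual values are summarised by visit as well as changes (SAP 6.2.2.1, 6.2.2.6 and 8.1), and an observed score at week 27 or 53 does not use day 1. SAP 4.4 defines titration and maintenance periods for analyses such as adverse events, so early events can be told from late ones. Protocol 9.6 also looks at ECG change from the parent baseline. All of this stands and narrows the point.

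**The day 1 distortion is not shown.** Every prior-drug patient has been off drug for at least 1 week, and some perhaps much longer. The amendment history shows that a 6-month rollover window applied between Amendment 02 (3 enrolled) and Amendment 04 (42 enrolled), so up to 42 - 3 = 39 patients may have entered under it. SAP 2.1 still gives both 4 weeks and 6 months, and these must be reconciled. Actual gaps are not reported. This stands too: r = 0 is compatible with the documents.

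**The target is long-term therapy, not first exposure.** The pooled incidence correctly describes the patients enrolled. It understates first-exposure risk only if it is read as that risk and if prior-drug patients do have fewer events; the documents establish neither. The mixture of histories remains.

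**The groups are small.** True, but the SAP already splits ECG abnormalities by four age groups (8.9) and titration dose by four weight groups and CYP2D6 status (5.7). Two columns of about 15-30 are larger on average, and well above the limit of 5 patients below which SAP 4.1 withholds means.

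**Everyone is re-titrated.** That aligns the dosing schedule, not the treatment history.

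**Conclusion.** The point holds as a gap in presentation that is cheap to close. The planned efficacy, adverse event, disposition and exposure summaries do not separate prior-drug from prior-placebo patients, although the protocol says that both enter.

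- **Adverse events and exposure.** This is the firmer half and bears on the primary objective. The two histories differ whatever the washout does. How far incidence differs is unknown; the 27-30% above is an illustration.
- **Change from day 1.** The mixture is possible, not proven. With a prior-drug share of 50-67% and 0-50% of the effect retained, all assumed, the pooled change is about 67-100% of the change from an untreated baseline. A rebound would take it above 100%.

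A reader might conclude that the pooled change must understate the drug's effect, or that parent randomisation already separates the two groups. Neither is supported. The documents show no residual effect or rebound at day 1. They describe the parent study as double-blind with placebo, but its randomisation is an inference and its allocation ratio is not stated.

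**What to change.** 1. **SAP 5.3:** add parent-study treatment (prior drug, prior placebo) as a baseline variable.
2. **SAP 6 and 8:** present change scores for MD-CRS, UHDRS-TMC and CGI-S, adverse events (at least for the titration period), discontinuations and dose changes by parent treatment and overall. Label the columns descriptive, and use the parent codes once unblinded. SAP 2.6.2 places the analyses after the end of this study, so the codes should be available by then; that is an inference.
3. **SAP 8.2:** add cumulative exposure from the first active dose in either study.
4. **SAP 8.11 and protocol 7.2.1:** define the C-SSRS breakdown by treatment as parent treatment, or remove it.

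The cost is a merge of parent treatment and dosing data, extra columns, and smaller groups: about 15-30 patients per column under the assumed allocations. No new patients, visits or assessments are needed, and the overall column stays as planned.
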